6.3.1.1 Dose Escalation criteria

The decision to advance from one dose level to the next dose level will only occur after careful evaluation of all the available safety and tolerability data for a given dose level by the Sponsor and Principal Investigators after completion of Cycle 1; data from later cycles of treated subjects may be taken into consideration in this decision.

Progression to the next higher dose will only occur if the previous dose level was deemed to be safe and well tolerated by the Principal Investigator and the Sponsor.

An appropriate interval ([REDACTED]) will separate the investigation of dose levels to permit a timely review and evaluation of safety data prior to proceeding to the next higher dose level.

When it is not appropriate to escalate the dose then the same dose, a previous dose or an intermediate dose may be given following discussion between the Principal Investigators and Sponsor. Additional dose levels may also be investigated depending upon the results of the safety data from the previous dose levels and consideration of the preclinical toxicology data.

All data reviewed at the dose escalation meeting between the Principal Investigators and Sponsor ([REDACTED]) will be subjected to a quality review.

In cases where more than one subject have been entered in the accelerated titration component of the study, only the 1st subject will be evaluable unless the Sponsor and Investigator deem otherwise. If the first subject enrolled in this cohort does not experience Grade 2 or higher AEs or DLTs during Cycle 1 of his/her study treatment (i.e., [REDACTED])

[figure not shown]
[REDACTED] the dose for the next subject(s) will be escalated to the next dose level. Enrollment into subsequent cohorts will proceed only after the current cohort has completed Cycle 1.

A subject administered a dose lower than the highest studied dose may have his/her dose increased up by one dose level at a time or to a dose that is 1 dose level below the highest studied dose, as per Investigator's discretion provided that:

1. The dose cohort to which the patient is being escalated has been completed (e.g., 1 cycle has been completed for all subjects).
2. The subject has not previously experienced a DLT.
3. The patient has no residual drug-related toxicity that is greater than grade 1.

Any results from intra-subject dose escalations will not affect inter-subject dose escalations unless the Investigator and Sponsor agree that intra-subject escalation information reasonably alters the potential benefit-risk ratio for subsequently treated subjects.

Dose escalations should occur at the beginning of a new cycle. Safety findings from intra-subject escalations will not be used for determination of the MTD of a regimen.

Abbreviations: D: Day, DLT: Dose limiting toxicity, MTD: Maximum tolerated dose.

In cases where more than 1 subject have been entered in the accelerated titration component of the study, only the 1st subject will be evaluable unless the Sponsor and Investigator deem otherwise. If this first subject enrolled experiences a Grade 2 or higher AE that is not clearly and incontrovertibly related to the underlying disease or concomitant medications, then that cohort and all subsequent cohorts will follow the standard 3+3 design. All toxicities will be considered when making decisions regarding drug escalation increments or discontinuations, unless they are clearly and incontrovertibly related to the underlying disease. When more than 1 subject is enrolled, enrollment may occur concurrently.

For the cohorts where the 3+3 design applies, 3 subjects will be enrolled initially. If there are no DLTs in the first 3 subjects, dose-escalation to the next higher dose level may proceed. If 1 of the 3 subjects experiences a DLT, that dose level will be expanded to 6 subjects (3 additional subjects will be enrolled). If 2 or more of 6 subjects at a given dose level experiences a DLT, the MTD will have been exceeded.

A DLT is defined as the occurrence of any of the following unless clearly and incontrovertibly related to the underlying disease. The hematological DLTs have been defined as per the Phase of CML:

- [REDACTED]
[REDACTED]
[REDACTED]
- Missed $\geq 25\%$ of doses over 28 days due to toxicity in Cycle 1
- Any grade of toxicity requiring dose reduction or discontinuation of IMP within the 28 day DLT assessment period [REDACTED]

Hematological DLT, as per the Phase of the Chronic Myeloid Leukemia:

- Hematological DLTs for subjects in CML-Chronic Phase
 [REDACTED] for ≥ 28 days off the study drug treatment or [REDACTED]
 [REDACTED] ≥ 7 days off the study drug (i.e.: after treatment interruption)
- Hematological DLTs for Subjects in CML-Accelerated Phase
 [REDACTED] for ≥ 28 days off the study drug treatment or [REDACTED]
 [REDACTED] ≥ 7 days off the study drug (i.e.: after treatment interruption) in the absence of features of accelerated phase (except cytogenetic changes) such as persistent increase in blasts or basophils
- Hematological DLTs for Subjects in CML-Blast Phase

[REDACTED]
 [REDACTED]
 [REDACTED]
 [REDACTED]
 [REDACTED]
 [REDACTED]
 [REDACTED]
 [REDACTED]
 [REDACTED]

Definition of the MTD: The MTD is defined as the dose that is 1 dose level lower than the dose at which a DLT is seen for [REDACTED] subjects administered the same dose of K0706 in Cycle 1 of therapy.

The MTD dose level will be expanded to [REDACTED] subjects, or if [REDACTED] subjects have already been enrolled and no more than [REDACTED] subjects experienced a DLT, then this lower dose level will be considered the MTD.

Subjects who experience a DLT and/or have a treatment delay may continue treatment in the absence of disease progression as long as the toxicity has recovered to the baseline value or lower.

A subject experiencing a DLT may continue therapy with a reduced dose of K0706. Subjects who experience a DLT and recover, may be treated (at the Investigator's discretion) at the next lower dose level until disease progression or other events requiring further dose reduction exist. For cohorts at Dose Level 2 or higher, a further dose reduction ([REDACTED]) may be implemented in the case of a further DLT or other non-DLT events requiring a dose reduction, if and when the event leading to dose reduction returns to Grade 1 or lower in severity. Further dose reduction or delay or both may be implemented basis joint discussion between Investigator and Sponsor's medical monitor basis evaluation of subject's clinical condition. The reduced dose may be re-escalated to the original or higher dose (i.e.: dose for which safety has been established in the dose escalation cohort) at Investigator's discretion considering subject safety and response to the study drug and in consultation with Sponsor's medical monitor. Subjects experiencing a Grade 4 toxicity attributable to K0706 will undergo dose reduction and dose delays as per guidance provided in Section 6.4.2.1. [REDACTED]
 [REDACTED].

Once [REDACTED] subjects experience a Grade [REDACTED] or [REDACTED] subject experiences Grade [REDACTED] toxicity (unless the AE is clearly and incontrovertibly related to underlying disease), further dose escalation steps will be reduced to [REDACTED] increments. The capsule composition of these doses will be assembled from the available capsule sizes and the selected dose will be rounded downwards rather than upwards to achieve a dose near the [REDACTED] increment. The capsules themselves will not be altered, only the combination of different capsules to be administered, [REDACTED]
 [REDACTED].

Definition of the RP2D: The RP2D will be the dose level selected for further evaluation; selection of the RP2D will be based on safety, tolerability, PD, preliminary anticancer activity findings, and the observed trough blood level for K0706 relative to levels found to be active preclinically.

6.3.1.2 Study Stopping Rules

The dose escalation in the study will be stopped when the MTD is reached or if continued evaluation of higher doses is not anticipated to add meaningful information for subsequent clinical development of the IMP for each planned cohorts in Part B or earlier if it is determined at any time that the risk benefit is unacceptable for any reason.

6.3.1.3 Discussion of Study Design

The study will be conducted in an open-label manner and all subjects will receive K0706. The rationale for the study and starting doses to be administered are presented in Section 6.1.

Appropriate safeguards for subject well-being and criteria for discontinuation of the K0706 in an individual subject and stopping rules are presented in Sections, 6.3.2.5, and 6.3.1.2 respectively.

An internal data monitoring committee consisting of members from the Sponsor, the investigative site, the CRO and an independent member will be formed to oversee the study. A formal charter will be generated that will describe the responsibilities of this group and submitted as an IND amendment prior to the initiation of Part B.

PK sampling and measurement of the drug concentrations will enable the assessment and comparison of the population PK profile of K0706. The duration of PK sampling has been chosen to sufficiently characterize the population PK of K0706.

In the study, due to the accelerated design, the cohort sizes will vary with [REDACTED] subjects being enrolled to each cohort. All subjects enrolled to the same cohort will receive the same dose level of K0706. Any specific subject will only be enrolled once, in a single cohort throughout the study. At least one and up to three subjects will be enrolled into each cohort following the accelerated design of the initial escalation steps. The subject(s) will receive the initial K0706 administration, and continue to receive K0706 at the same dose daily. This single dose level accelerated escalation will proceed to the next dose level unless there are Grade [REDACTED] or higher AEs or DLTs within the cohort's [REDACTED] observation period. In cases where more than 1 subject have been entered in the accelerated titration component of the study, only the 1st subject will be evaluable unless the Sponsor and Investigator deem otherwise. If the 1st enrolled subject experiences a Grade [REDACTED] or higher AE that is not clearly and incontrovertibly related to the underlying disease 2 or concomitant medications, additional subjects will be enrolled at that current dose. That cohort and all subsequent cohorts will follow the standard 3+3 design. All toxicities will be considered when making decisions regarding drug escalation increments or discontinuations, unless they are clearly and incontrovertibly related to the underlying disease. When more than 1 subject is enrolled, enrollment may occur concurrently and the subjects may be administered K0706 concurrently.

6.3.2 Study Population

Up to approximately [REDACTED] subjects will be enrolled. This number includes the dose-escalation cohorts and the sub-group expansion cohorts.

Up to approximately [REDACTED] subjects will be enrolled in the dose escalation phase. Up to approximately [REDACTED] subjects will be enrolled in the sub group expansion cohorts. In case the MTD is not defined within the predefined dose levels, more subjects may be enrolled.

[figure not shown]
Subjects with Ph+ CML-CP, Ph+ CML-AP, Ph+ CML-BP or Ph+ ALL will be entered into the study provided that they satisfy the inclusion/exclusion criteria presented in Section 6.3.2.1.1 and 6.3.2.1.2.

6.3.2.1.1 Subject Inclusion Criteria

Subjects may be included in the study if they meet all of the following criteria:

1. Willing and able to give written/signed, and dated, informed consent (or by legally acceptable representative/impartial witness when applicable inclusion of subjects needing legally acceptable representative/impartial witness will be in compliance to the enrolling country's regulatory requirement) and is available for the entire study.
2. Willing and able to comply with the scheduled visits, treatment plan, laboratory testing, study procedures, and restrictions and be accessible for follow-up
3. Subjects diagnosed with Ph+ CML-CP, Ph+ CML-AP, Ph+ CML-BP or Ph+ ALL who are refractory or intolerant to at least 3 TKIs or are not eligible (e.g.: due to comorbidities, hypersensitivity to excipients, lack of insurance coverage) for their local country's regulatory approved and medically appropriate TKIs (e.g.: a TKI that is effective against mutations in the patient's tumor)
4. Male or female aged ≥ 18 years
5. Eastern Cooperative Oncology Group (ECOG) performance status of 0, 1, or 2
6. [REDACTED]

| | |
|------------|------------|
| [REDACTED] | [REDACTED] |
| [REDACTED] | [REDACTED] |
| [REDACTED] | [REDACTED] |
| [REDACTED] | [REDACTED] |
| [REDACTED] | [REDACTED] |
| [REDACTED] | [REDACTED] |
| [REDACTED] | [REDACTED] |
| [REDACTED] | [REDACTED] |
| [REDACTED] | [REDACTED] |
| [REDACTED] | [REDACTED] |

7. Subjects of childbearing potential must practice an medically acceptable method of birth control as judged by the Investigator:
- a. Medically acceptable methods of birth control include the use any of the effective birth control methods listed below –
 - i. Combined (estrogen and progestogen containing) hormonal contraception associated with inhibition of ovulation (oral, intravaginal, transdermal)
 - ii. Progestogen-only hormonal contraception associated with inhibition of ovulation
 - iii. Placement of an IUD/ intra-uterine hormone releasing system. Consideration should be given to the type of device or system being used, as there are higher failure rates quoted for certain types, e.g., steel or copper wire
 - iv. intrauterine hormone-releasing system (IUS)
 - v. same sex partner, a vasectomized partner/bilateral tubal occlusion
 - b. The contraceptive should have been used continually within the past 3 months and the subject has to agree to continued use during the study and for 3 months after the last IMP administration.
 - c. To adopt another birth control method, or a double-barrier method which consists of a combination of any 2 of the following: diaphragm, cervical cap, condom, or a spermicide. The barrier method must be used in combination with another highly effective, non-barrier method (such as mentioned in Inclusion criteria # 7a) for at least 2 months prior to study entry and must continue to use contraception for the duration of the study and for 3 months after the last IMP administration.

- d. Subjects who are postmenopausal for at least 1 year based on history and Investigator's opinion or surgically sterile (bilateral tubal ligation, bilateral oophorectomy, or hysterectomy has been performed on the subject). For women < 45 years with menopausal symptoms, the menopause status to be reconfirmed by suitable laboratory tests including FSH level.
8. Male subjects enrolled in the study should not father a child and are advised to prevent passage of semen to their sexual partner during intercourse using an acceptable method as detailed in the Inclusion criteria # 7 and judged by the Investigator for the duration of the study and for 3 months after the last IMP administration
9. Female subjects of childbearing potential must have a negative pregnancy test (as confirmed by a negative urine pregnancy test with a sensitivity of less than 50 mIU/mL or equivalent units of human chorionic gonadotropin).
10. Female subjects must be non-lactating and non-breast-feeding

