7.3.1.4 Trial End points

7.3.1.4.1 Primary Endpoints

- Cohort A: For CML subjects in CP at study entry: major cytogenetic response (MCyR), defined as complete cytogenetic response (CCyR) or partial cytogenetic response (PCyR).
(CP subjects in CCyR are not eligible for this study)
- Cohort B: For CML subjects in AP at study entry: major hematologic response (MaHR), defined as complete hematologic response (CHR) or no evidence of leukemia (NEL). (AP subjects in MaHR are not eligible for this study)
- Cohort C: For CML subjects in BP at study entry: MaHR, consisting of CHR or NEL. (BP subjects in MaHR are not eligible for this study)

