8 DEMOGRAPHIC AND OTHER BASELINE CHARACTERISTICS

The safety analysis set will be used to summarize the subjects' demographics and baseline characteristics. Continuous variables (e.g., age and weight) will be summarized [REDACTED]

[REDACTED] Qualitative variables (e.g., sex, race, and ethnicity) will be summarized [REDACTED].

The demographic parameters will include age category (<65 and ≥65 years), gender, race, ethnicity. Age will also be summarized as a continuous variable. The baseline parameters include, ECOG performance status, weight, height, body mass index, ECOG performance status, baseline cardiovascular and metabolic co-morbidities. Also included will be baseline TKI status (Refractory, intolerant and resistant), history of bone marrow transplantation, baseline Ph+ cells, number of prior TKIs received, prior ponatinib treatment, prior ponatinib and asciminib treatment, baseline mutation status, extramedullary involvement (Yes/No) and baseline cytogenetic (i.e: complete or partial) and molecular responses (by BCR::ABL1 transcript %). Additionally, data will be separately presented by disease type and dosing cohorts.

By-subject listings of demographic and other baseline characteristics will be provided for safety analysis set.

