used. When central laboratory data is not available, then data from the local laboratory will be used for the analysis. [REDACTED]

[REDACTED]

Molecular Response:

Molecular response is assessed using quantitative PCR (qPCR) based on the amount of BCR-ABL protein in the blood and is presented below in Table 2.

[REDACTED]

[REDACTED]

[REDACTED]

[REDACTED]

[REDACTED]

Cytogenetic, molecular, and hematologic responses will be summarized [REDACTED]

[REDACTED]

[REDACTED]

[REDACTED]

Criteria for Molecular Responses

[REDACTED]

Cytogenetic, molecular, and hematologic responses will be summarized [REDACTED]

[REDACTED]

Cytogenetic, molecular and hematological responses [REDACTED] will be presented [REDACTED]. The response rate at a specific time point is defined as the number of subjects who achieved the response at that time point divided by the total number of subjects in the treatment group. [REDACTED]

[REDACTED] The hematological

response will be summarized only for subjects with CML-AP and BP.

A separate summary will be provided for the best cytogenetic and molecular responses by achieved and maintained responses during the study period. The assessment for the achieved response includes all subjects who entered the study without the specific response. The assessment for the maintained response includes subjects who entered the study with the specific response.

By-subject listings of pharmacodynamic parameters will be provided for the safety analysis set. A by-subject listings will be provided for subjects who had disease progression.

Time to CCyR/MMR (in weeks), defined as the date of first documented CCyR/MMR - date of randomization + 1 divided by 7 will be summarized descriptively using number of subjects, mean, SD, median, minimum, maximum and quartiles.

Duration of CCyR/MMR, defined as the time between the date of the first documented MMR to the earliest date of confirmed loss of MMR or progression to accelerated phase (AP)/BP, or CML-related death will be summarized descriptively. The duration of CCyR/MMR (in weeks) is calculated as (end date or censoring date of CCyR/MMR - date of first CCyR/MMR + 1)/7.

All analysis will be conducted separately for all CML subjects and CML-CP subjects.

Further analyses for efficacy may be performed by dose group, stage of CML, resistance or intolerance, and mutational status.

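### The SAP does not restrict time to and duration of CCyR/MMR to subjects who lacked the response at baseline, and the readable Part B criteria do not bar subjects who already have it

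*Protocol*

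**What the plan says.** **Part B entry.** Protocol 6.3.2.1.1, criterion 3, admits subjects "who are refractory or intolerant to at least 3 TKIs or are not eligible" for locally approved and appropriate TKIs. None of the readable criteria in 6.3.2.1.1 or 6.3.2.1.2 sets a minimum disease burden or bars CCyR or MMR at entry. Inclusion 6 and exclusions 14 and 16 are blacked out.

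**Part C, for contrast.** Protocol 7.3.1.4.1 states that "CP subjects in CCyR are not eligible for this study". Protocol 7.8.1 adds that a subject entering in PCyR must reach CCyR to count as a responder.

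**The SAP plans for baseline responders.** SAP Section 8 lists "baseline cytogenetic (i.e: complete or partial) and molecular responses" among the baseline characteristics. The SAP efficacy text that follows Section 10 (its own heading is blacked out) says: "A separate summary will be provided for the best cytogenetic and molecular responses by achieved and maintained responses during the study period". Its *achieved* group is made up of those who lacked the response in question at entry. For the other group it says: "The assessment for the maintained response includes subjects who entered the study with the specific response".

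**Time to and duration of response.** The same text goes on to time to CCyR/MMR, "defined as the date of first documented CCyR/MMR" less a date of randomization, plus one day, in weeks. Duration runs from the date of first CCyR/MMR to its end or censoring date, plus one day, in weeks. Both are to be summarized descriptively. The only populations named are all CML and chronic-phase CML. The efficacy set in SAP 5.4 is everyone dosed.

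**The concern.** A subject who enters in CCyR or MMR has no time to that response to measure. Any value the formula returns is a sampling date: the screening test if it counts, otherwise the first on-study test. Pooling these values with those of subjects who reached the response on K0706 pulls the summary down. Duration has an attribution problem, because part of what it measures continues a response produced by earlier treatment.

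The SAP recognises the distinction for best response and then does not carry it into the two time-based measures. Part B has no formal test, so no error rate or sample size is at stake. What is at stake is whether a quoted time to response or duration describes the drug or, in part, the mix of subjects enrolled.

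**Working it through.** The documents give no figure for time to or duration of response and no count of baseline responders, so there is nothing to reproduce. The check reads the definitions and then illustrates their behaviour.

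**1. Does anything in the definitions exclude a baseline responder?**
- The achieved/maintained split is attached to a separate summary of best response.
- The time-to and duration sentences name no baseline condition and do not say that the first response must be post-dose.
- A pre-dose result will exist: Protocol 6.7.2 provides for a screening marrow in Part B, including one taken as standard care before consent.
- The stated time origin does not exist in Part B, because Protocol 6.4.8 says subjects are not randomized. No first-dose anchor therefore rules out a pre-dose date.

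**2. What the formula returns for one baseline responder** (first dose used as origin):
- sample 2 weeks before dosing: (−14 + 1)/7 = −1.9 weeks
- first test at week 12: (84 + 1)/7 = 12.1 weeks

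**3. Time to response in a pooled group.** Assumptions: tests every 12 weeks; new responders first respond at weeks 12, 24, 36 and 48 with shares 0.4, 0.3, 0.2 and 0.1; baseline responders are a share f of all counted responders.

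New responders only: 0.4×12 + 0.3×24 + 0.2×36 + 0.1×48 = 24, plus 1/7 = 24.1 weeks.

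Pooled mean = 24(1 − f) + b·f + 1/7, where b = −2 if the screening sample counts and b = 12 if only post-dose samples count.

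| f | screening sample counts | post-dose only |
|---|---|---|
| 0.10 | 21.5 | 22.9 |
| 0.30 | 16.3 | 20.5 |
| 0.50 | 11.1 | 18.1 |

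The mean falls in every row. The median behaves differently. With b = 12, the cumulative share at week 12 is f + 0.4(1 − f), which reaches 0.5 at f = 0.1/0.6 = 0.17. Below that the median stays at about 24 weeks; above it, it drops to about 12. With first-response shares of 0.3, 0.3, 0.2 and 0.2 instead, the threshold is 0.2/0.7 = 0.29.

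**4. Duration.** Further assumptions: cut-off at week 104 and exponential loss of response with median m. A response starting at week s then has mean observed duration (1 − exp(−λ(104 − s)))/λ, with λ = ln 2/m. Censored values are averaged in as the SAP formula produces them. The one-day term is left out because it adds the same 1/7 week throughout.

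Check at m = 52: starts at weeks 12, 24, 36 and 48 give 53.0, 49.2, 44.7 and 39.5, weighted mean 48.9. With f = 0.3 and equal loss rates, pooling gives 0.7×48.9 + 0.3×53.0 = 50.1 (start at week 12), or 0.7×48.9 + 0.3×56.8 = 51.2 (start 2 weeks before dosing).

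| m (weeks) | new responders only | pooled, f = 0.3, equal loss | loss hazard ratio above which pooling shortens the mean |
|---|---|---|---|
| 52 | 48.9 | 50.1 to 51.2 | 1.17 to 1.28 |
| 104 | 61.8 | 63.9 to 66.1 | 1.40 to 1.70 |
| 208 | 70.1 | 72.8 to 75.9 | 1.87 to 2.53 |

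In each range the first figure is for a start at week 12 and the second for a pre-dose start. The rise comes from starting the clock earlier before a common cut-off. With equal loss rates the median moves by less than one week.

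**The case against.** **The SAP never says that baseline responders are included.** A reader might infer that these measures are taken in all subjects. That rests on silence plus the all-dosed efficacy set. The achieved/maintained split stands just before the definitions, and a programmer could carry it over. This is fair: inclusion is the literal reading, not a stated rule. But the split is expressly tied to best response, and an endpoint definition should not depend on a guess.

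**Zero or negative times are doubtful for CCyR.** Protocol 7.5.2.2 describes cytogenetic response as a reading taken after K0706 has been given, which would rule out a screening sample. That is Part C text and does not cover MMR, and the matching Part B section (6.5.2.2) is partly blacked out. A first post-dose test would still be logged as a time to response.

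**Redaction.** Part B criteria and parts of the SAP response text cannot be read, so a bar or a dating rule might sit there. This limits certainty. A hidden bar is unlikely, because a maintained group for cytogenetic and molecular response would then have little purpose.

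**Longer duration is not established.** A reader might infer that the error favours the drug in both measures. The documents fix neither the start date nor the relative rate of loss, and the direction can reverse.

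**Low stakes.** Time to and duration of response are named endpoints of Part C (Protocol 7.3.1.4.2), where chronic-phase subjects in CCyR are barred. Part B lists only a general anti-leukemic response assessment (Protocol 6.8.1) and no formal testing. This stands, and it limits the weight of the point.

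**Conclusion.** The gap is real and lies in the SAP efficacy text; the Part B eligibility wording supplies the premise and is not itself at fault. If the definitions are applied as written, baseline responders shorten the reported mean time to response under every assumption tried. Duration partly reflects a response obtained before K0706, whichever way its mean moves.

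The size cannot be stated. Under the assumed visit pattern, mean time to response falls from 24.1 weeks by 1.2 weeks (10% share, post-dose samples only) to 13.0 weeks (50% share, screening sample counted). The median may not move at all at low shares. For duration, a 30% share with equal loss rates raises the mean by about 1 to 6 weeks, and the sign reverses once baseline responders lose response fast enough.

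The documents do not support the stronger claim that these summaries would largely describe who was enrolled. That needs a share of baseline responders which they do not give. The outputs affected in Part B are descriptive, so this is a correction worth making before the analysis, not a threat to the trial's primary conclusions.

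**What to change.** In the SAP efficacy text that defines time to and duration of CCyR/MMR:

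1. Restrict both measures to subjects without that response at baseline, the SAP's own *achieved* group, applied separately for CCyR and for MMR.
2. Require the first response to come from a post-dose sample.
3. Count time from first dose, since Part B has no randomization date.
4. Report subjects who entered with the response separately, as duration of maintenance from first dose, with their number.

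The cost is a sentence or two in the SAP and one extra table, with no new data. The downside is fewer subjects in these summaries and possibly a longer reported time to response. If the sponsor already intends this restriction, the change only records it.
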